#### 4.1.8 Ambulatory blood pressure monitoring Full analysis set

The aFAS includes all subjects from the FAS who have a baseline 24 h mean SBP, measured by ABPM with a total duration of at least 21 hours and at least 70% valid readings [Section 6.4.1]. Subjects will be evaluated according to their assigned study treatment in the DB part.

#### 4.1.9 Modified ambulatory blood pressure monitoring Full analysis set

The maFAS includes all subjects from the mFAS who have a DB-WD baseline 24 h mean SBP, measured by ABPM with a total duration of at least 21 hours and at least 70% valid readings [Section 6.4.1]. Subjects will be evaluated according to their assigned study treatment in the DB-WD part.

#### 4.1.10 Safety analysis set

The SAF includes all randomized subjects who received at least one dose of study treatment in the DB part. Subjects will be evaluated according to the study treatment they received in the DB part. In the unlikely event that a subject received different treatments in the DB part, actual treatment will be set to the highest dose of aprocitentan that subject received (12.5 mg or 25 mg).

#### 4.1.11 Restricted Safety analysis set

The subset of subjects from the SAF who received at least one dose of study treatment in the SB aprocitentan part will be referred to as the rSAF.

#### 4.1.12 Modified Safety analysis set

The mSAF includes subjects from the SAF who received at least one dose of study treatment in the DB-WD part. Subjects will be evaluated according to the study treatment they received in the DB-WD part. In the unlikely event that a subject received different treatments in the DB-WD part, actual treatment will be set to be aprocitentan 25 mg.

#### 4.1.13 Pharmacokinetic set

The PK set includes all subjects from the SAF who received at least one dose of aprocitentan, had evaluable plasma concentrations and did not violate the protocol in a way that might affect the evaluation of the PK endpoint.

Reasons for exclusion from the PK set are:

- DB treatment duration less than 21 days.
- Compliance with DB treatment < 80% or > 120% [as calculated in Section 5.5.2].
- AOBPM not done at trough at Week 4 (V6) as per protocol deviation list code 03F20.
- PK samples not collected at Week 4 (V6) as per protocol deviation list code 03F26.

#### 4.2 Usage of the analysis sets

The role of the analysis sets in each of the study parts (DB, SB aprocitentan and DB-WD) is summarized in Table 3.

**Table 3 Role of the analysis sets**

Study part	DB	SB aprocitentan	DB-WD
Efficacy endpoints based on AOBPM	FAS (PPS)	–	mFAS (mPPS)
Efficacy endpoints based on ABPM	aFAS	–	maFAS
Safety endpoints	SAF	rSAF	mSAF
Pharmacokinetic endpoints	PK	–	–

ABPM = ambulatory blood pressure monitoring; aFAS = ABPM Full analysis set; AOBPM = automated office blood pressure measurement; DB = double-blind; FAS = Full analysis set; maFAS= modified ABPM Full analysis set; mFAS = modified Full analysis set; mPPS = modified Per-protocol set; mSAF = modified Safety analysis set; PK = pharmacokinetic; PPS = Per-protocol set; rSAF = restricted Safety set; SAF = Safety analysis set; SB = single-blind; WD = withdrawal.

Descriptive statistics for selected efficacy and safety endpoints during the RI period will be based on the RIS. The SCR will be used for subject listings.

## 5 STUDY SUBJECT VARIABLES AND ANALYSES

### 5.1 Subject disposition

#### 5.1.1 Study disposition

A subject is considered:

- Screened: if the subject has given informed consent to participate in the study and has received a subject number.
  - A screening failure is defined as a screened subject who did not enter the run-in. The reason for screening failure is collected in the **Run-in Enrolment eCRF**. Subjects who failed screening twice will only be counted once (and only the reason for the last screening failure will be tabulated).
- To have entered the RI period: if the subject received at least one dose of RI treatment (placebo) according to the **Study Treatment Log**.
  - A run-in failure is defined as a subject in run-in who was not randomized. The reason for run-in failure is collected in the **Randomization eCRF**.
- Randomized: if the subject was assigned a randomization number by the IRT system at Visit 4.
  - A DB drop-out is defined as a randomized subject who did not enter the SB aprocitentan part.
- To have entered the SB aprocitentan part if the subject received at least one dose of SB aprocitentan according to the **Study Treatment Log**.
  - A SB aprocitentan drop-out is defined as subject in the SB aprocitentan part who was not re-randomized. The reason for not being re-randomized is collected in **Re-Randomization eCRF**.
- Re-randomized: if the subject was assigned a re-randomization number by the IRT at Visit 11.
  - A DB-WD premature treatment discontinuation is defined as a re-randomized subject who did not complete study treatment.
- To have completed study treatment: if on the **Study Treatment Log** Study period is 'Double-blind Withdrawal Treatment (Part 3)' and Reason for treatment stop is 'Completion as per protocol'.
- To have completed the study: when this is indicated on the **End of Study Status eCRF**.

A disposition graph in the clinical study report will display the numbers of subjects in each category defined above. Subjects will be displayed according assigned study treatment,

where applicable. Any difference between assigned and actual treatment will be added in footnotes.

The number (%) of screening failures (i.e., subjects screened but not in RI) will be calculated based on the SCR. Reasons for not being enrolled in the RI period as collected on the **Enrollment** eCRF will be tabulated for the SCR. All eligibility criteria not met during screening and run-in period and eligibility criteria not met grouped by category of inclusions/exclusions criteria and standardized background antihypertensive therapy status will be summarized on the SCR.

The number (%) of RI failures (i.e., subjects in RI but not randomized) will be calculated based on the RIS. Reasons for not being randomized as collected on the **Randomization** eCRF (Part 1) will be tabulated for the RIS.

The numbers of subjects randomized and re-randomized will be tabulated by treatment group for the FAS and mFAS, respectively. Reasons for not being re-randomized as collected on the **Randomization** eCRF (Part 3) will be tabulated for the FAS.

The numbers of subjects screened, in run-in, randomized and re-randomized will also be provided by country and site.

### 5.1.2 Study completion/discontinuation

A subject is considered to have prematurely discontinued the study when this is indicated on the **End of Study Status** eCRF. Reasons for premature study discontinuation are collected on the same form and include: withdrawal by subject, AE, lost to FU, death, and other. If the reason for premature study discontinuation was related to the COVID-19 pandemic, this was collected.

Reasons for premature study discontinuation in the RI period will be summarized based on the RIS. Reasons for premature study discontinuation in the randomized treatment period will be summarized for the RND. Reasons related to the COVID-19 pandemic will be included in these summaries and will also be listed as such.

### 5.1.3 Study treatment completion/discontinuation

A subject is considered to have prematurely discontinued treatment in the RI period if on the **Study Treatment Log** the 'Study period' is 'Single-Blind Run-in' and 'Reason for treatment stop' is 'Discontinued'.

A subject is considered to have prematurely discontinued study treatment in the DB (SB aprocitentan, DB-WD, respectively) part if on the **Study Treatment Log** the 'Reason for treatment stop' is 'Discontinued' for the corresponding 'Study period'.

Reasons for premature discontinuation are collected on the same form and include: AE, lack of efficacy, withdrawal by subject, lost to FU, death, pregnancy, and other. If the

reason for premature study treatment discontinuation was related to the COVID-19 pandemic, this was collected.

The numbers of subjects treated in the DB, SB aprocitentan and DB-WD parts will be tabulated by treatment group in the SAF, rSAF and mSAF, respectively.

The number (%) of subjects with and the reasons for premature treatment discontinuation in the RI period will be summarized based on the RIS.

The number (%) of subjects with and the reasons for premature treatment discontinuation in the randomized treatment period will be summarized by study part and treatment group (within study part) in the SAF, rSAF or mSAF, where appropriate. Reasons for premature study treatment discontinuation related to COVID-19 pandemic will also be summarized.

## 5.2 Protocol deviations

The number (%) of subjects with all PDs and important PDs (as per PD code list) will be summarized by treatment group and by study part DB+SB and DB-WD based on the FAS (for DB+SB) and based on the mFAS (for DB-WD). In addition, the same summaries of all PDs and important PDs will be provided separately for PDs related to the COVID-19 pandemic as per FDA guidance.

## 5.3 Exclusion from analysis data sets

The number (%) of subjects excluded from the PPS and the reasons for exclusion [Section 4.1.6] will be tabulated by treatment group based on the FAS. The number (%) of subjects excluded from the mPPS the reasons for exclusion [Section 4.1.7] will be tabulated by treatment group based on the mFAS.

The number (%) of subjects excluded from the PK set and reasons for exclusion will be tabulated by treatment group based on the SAF.

## 5.4 Subject characteristics

Subject characteristics are obtained at Screening (i.e., Visit 1). If a subject was re-screened and a value changed between Screening and Re-screening, the value at Re-screening should be used.

### 5.4.1 Demographics

Demographic variables include age, sex, race and ethnicity as collected at Screening on the **Demographics** eCRF form as well as country and region.

Age will also be categorized as 18–< 65, 65–< 75 and  $\geq 75$  years.

Country will be derived from site number.

Region is provisionally defined as:

- Asia/Australia (Australia, China, South Korea),
- Europe (Belgium, Czech Republic, Denmark, Finland, France, Germany, Italy, Hungary, Lithuania, Netherlands, Poland, Russia, Spain, Ukraine, United Kingdom, Israel and Greece), and
- North America (Canada, US).

Each of these three regions has at least 50 subjects [section 2.2.5 of [ICH 2017a](#)].

Other demographic variables include:

- Height and body weight (converted into cm and kg, respectively, if applicable)
- Body weight at baseline will also be categorized as  $\leq 100$  kg,  $>100$  kg
- BMI at screening where  $BMI = \text{weight}[\text{kg}]/(\text{height}[\text{cm}]/100)^2$
- BMI at screening will also be categorized as  $< 25$ ,  $25- <30$ ,  $30- <40$  and  $\geq 40$  kg/m^2

Demographic variables will be summarized by treatment group as well as overall in the DB and DB-WD periods for the FAS and mFAS, respectively. For European Clinical Trials Database (EudraCT) purposes, the number of subjects treated in each age category ( $< 18$ ,  $18- <65$ ,  $65- <85$  and  $\geq 85$  years at Screening) will be summarized for the FAS and mFAS.

#### 5.4.2 Disease characteristics

Disease characteristics include:

- Time from first diagnosis of hypertension [years] = (date of Visit 1 – date of diagnosis)/365.25 (from the **Hypertension History** eCRF) at Screening.
- Number of antihypertensive therapies present at screening [as defined in Section 5.4.4];  $<3$ , 3, 4 and  $\geq 5$
- SiSBP and sitting diastolic BP (SiDBP) as measured by AOBPM at screening
- UACR;  $< 30$  mg/g,  $30-300$  mg/g,  $> 300$  mg/g at Baseline.
- (eGFR;  $< 30$ ,  $30- < 45$ ,  $45- < 60$ ,  $\geq 60$  mL/min/1.73 m^2) according to the CKD-EPI equation [[Levey 2009](#)] at Baseline.

Disease characteristics will be summarized by treatment group as well as overall in the DB and DB-WD periods for the FAS and mFAS, respectively.

#### 5.4.3 Medical history

Medical history collected at Screening will be coded using MedDRA. Previous diseases/procedures are medical history where ‘Ongoing at informed consent signed’ is ‘No’ on the **Medical History** eCRF. Ongoing diseases/procedures are medical history

where ‘Ongoing at informed consent signed’ is ‘Yes’. If the response to ‘Ongoing at Informed consent’ is missing, then the disease/procedure is considered as ongoing.

Medical history will be summarized by SOC, PT and treatment group as well as overall in the FAS. This will be done separately for previous and ongoing diseases/ procedures.

#### 5.4.4 Previous and concomitant therapies

Therapies are collected in the **Previous/Concomitant Medications** eCRF, and terms are coded using the WHO Drug code dictionary and the ATC class code using the versions available at database lock.

Previous therapy is medication for which the end date is prior to the date of first randomization. If the end date is (partially) missing, the imputation rules from Section 10.2.2 will be applied.

Concomitant therapy is any medication that is ongoing at Randomization or initiated during the randomized treatment period. In particular:

- DB study treatment concomitant therapies are treatments that are either ongoing at the start of DB study treatment or initiated during the DB treatment part.

SB study treatment concomitant therapies and DB-WD study treatment concomitant therapies are defined similarly. Rules for handling (partially) missing dates are detailed in Section 10.2.2.

A study-concomitant therapy is medication that is ongoing at or initiated after signing of informed consent or initiated up to 30 days after EOT.

The number (%) of subjects having taken at least one concomitant medication will be summarized by ATC classification level 4 and individual preferred name within each ATC classification by study part. Concomitant therapy will be sorted by ATC class and preferred name within each ATC class by descending frequency based on all treatment groups combined.

All study-concomitant medication will be listed, where ‘treatment’-concomitant medication will be flagged.

Individual antihypertensive therapies stopped or ongoing during screening period by ATC classifications will be summarized based on the FAS. The following categories will be shown in the table:

- Renin-angiotensin system blockers divided in 2 categories:
  - Angiotensin-converting enzyme inhibitor (ACEi).
  - Angiotensin receptor blockers (ARB).

- Calcium channel blockers (CCB).
- Diuretics
  - Mineralocorticoid receptor antagonist (MRA).
- Beta-blockers.
- Centrally acting antihypertensives.
- Others in combination [as defined in Appendix 14.4].
- Others.

## 5.5 Study treatment duration and compliance

### 5.5.1 Treatment duration

Randomized treatment duration (in days) is defined separately for the DB, SB aprocitentan and DB-WD parts as the date of the last dose of treatment in the DB (SB aprocitentan, DB-WD, respectively) part minus the date of the first dose in the DB (SB aprocitentan, DB-WD, respectively) part plus one day, ignoring treatment interruptions. The detailed derivations based on the **Study Treatment Log** are given in Section 10.1.1. Randomized treatment duration will also be expressed in weeks.

RI treatment duration is defined as the date of the last dose of SB placebo minus the date of the first dose of SB placebo plus one day [see Section 10.1.1].

Standardized background antihypertensive therapy duration in the RI period as well as in the DB, SB aprocitentan, and DB-WD parts is defined similarly based on the **Standardized Background Antihypertensive Therapy Log**.

Treatment duration (in days as well as weeks) will be summarized by study part and treatment group (within study part) in the SAF, rSAF and mSAF, respectively. Total exposure (in subject-years, where a year equals 365.25 days) will also be summarized by study part and treatment group.

Time from first dose of DB treatment to (premature) treatment discontinuation in the DB or SB aprocitentan part will be summarized by treatment group using Kaplan-Meier plots (supplemented with a table displaying the numbers of subjects at risk, with an event, and censored by treatment group, using weekly intervals) in the SAF. For subjects who completed the treatment, time to discontinuation will be censored at the last dose of SB treatment (or at the last dose of DB treatment if the subject did not enter the SB part). Additionally, a ‘two-step’ Cox model with a factor for treatment in the DB part will be fitted. This model allows for different treatment effects in the DB and SB aprocitentan parts. The treatment effect in the latter part (if any) is expected to be smaller than in the former part [for details, see Section 8.2].

Time from first dose of DB-WD treatment to (premature) treatment discontinuation in the DB-WD part will be summarized similarly in the mSAF, except that the Cox model is the conventional one.

RI treatment duration will be summarized based on the RIS. Standardized background antihypertensive therapy duration will be summarized by study part and treatment group (within study part) in the SAF, rSAF and mSAF, respectively.

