**Figure 1 Study design**

EOT = End-of-Treatment; FU = follow-up; V = visit.

The randomized treatment period lasts for 48 weeks [until EOT, as displayed in Figure 1]. The purpose of this period is to evaluate the primary and secondary objectives of the study. This period consists of three sequential parts:

- In the first DB part of 4 weeks, subjects will be randomized to aprocitentan 25 mg, aprocitentan 12.5 mg or placebo in a 1:1:1 ratio.
- In the second SB part of 32 weeks, all subjects will receive aprocitentan 25 mg.
- In the third DB-WD part of 12 weeks, subjects will be re-randomized at Week 36 to aprocitentan 25 mg or placebo in a 1:1 ratio.

The EOT visit will take place at Week 48 (i.e., end of DB-WD part) or earlier in the event of premature discontinuation of study treatment.

Approximately 4000 subjects were expected to be screened in order to enroll approximately 1500 subjects with a diagnosis of RHT into the SB placebo RI period. At least 600 subjects were to be randomized and at least 380 subjects were expected to be re-randomized in the DB-WD part. At least 300 subjects were expected to complete the study (including the 30-day safety FU period). The study was to be conducted at approximately 100 sites in approximately 20 countries.

The sponsor planned to look at the drop-out rate (between Randomization and Re-randomization) nine months after the randomization of the 200th subject.

If the observed drop-out rate was such that the expected number of subjects to be re-randomized in the DB-WD part was less than 380, the number of subjects randomized could have been increased to maintain at least 85% power for the DB-WD part (which is

achieved when 324 subjects are re-randomized). It appeared that the drop-out rate was lower than expected, so no sample size increase was needed to compensate for drop-out.

Ultimately, 730 subjects were randomized. The overrunning was caused by the addition of sites and countries in 2020 meant to compensate for the lower recruitment due to the Covid-19 pandemic. In order to give these new sites a reasonable chance to contribute to the study, the timelines were prolonged, which, combined with a surge in screening when the EOS was announced, lead to an over-recruitment. The study was finally conducted at 193 sites in 22 countries.

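### Time to treatment discontinuation over DB plus SB censors subjects who complete DB but never start SB, so any such permanent stop is left out of the curve and the two-step Cox model

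*SAP*

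**What the plan says.** SAP section 5.5.1 sets up one time-to-event endpoint across two study parts: "Time from first dose of DB treatment to (premature) treatment discontinuation in the DB or SB aprocitentan part will be summarized by treatment group". It is analysed in the safety analysis set (SAF) with Kaplan-Meier plots and a two-step Cox model. The censoring rule is "For subjects who completed the treatment, time to discontinuation will be censored at the last dose of SB treatment", with the added clause "or at the last dose of DB treatment if the subject did not enter the SB part".

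Three other places bear on the same subject:

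- **Section 5.1.1, flow category.** "A DB drop-out is defined as a randomized subject who did not enter the SB aprocitentan part".
- **Section 5.1.1, completion.** Completed study treatment is reserved for subjects whose log shows "Study period is 'Double-blind Withdrawal Treatment (Part 3)' and Reason for treatment stop is 'Completion as per protocol".
- **Section 5.1.3, the event.** Premature discontinuation in a part requires that the log shows "Reason for treatment stop' is 'Discontinued' for the corresponding 'Study period".

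On the time scale, section 2.1 gives 4 weeks of DB and then "In the second SB part of 32 weeks, all subjects will receive aprocitentan 25 mg". The same section puts the end-of-treatment visit at Week 48, or sooner only when study treatment is prematurely discontinued.

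**The concern.** A subject who takes the last DB dose at about Week 4 and takes no SB dose has permanently stopped study treatment, and the stop falls inside the period that the curve covers. Censoring that subject makes Kaplan-Meier and Cox assume the subject would have persisted like those who continued. Here the reason for censoring is itself the outcome being measured.

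Two outputs are at stake. One is the retention curve to Week 36. The other is the set of DB-interval hazard ratios, because these stops fall exactly at the DB/SB boundary, which is the last point at which the arms have been on different treatments.

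**Working it through.** **Step 1: which subjects the rule reaches.** Take a treated subject with no SB dose.

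| DB log entry | Section 5.1.3 | Section 5.5.1 | Section 5.1.1 |
|---|---|---|---|
| Discontinued | premature discontinuation in DB | event | DB drop-out |
| Completed | event in neither part | censored at last DB dose | DB drop-out; has not completed study treatment |

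Only the second row is a problem. Under the section 5.1.1 definition of completion, the added clause in 5.5.1 would describe nobody, since a subject who skipped SB cannot have completed Part 3. The clause therefore has meaning only if completion refers to the DB part, and on that reading it censors a permanent stop.

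**Step 2: closed form.** The SAP states no figure for this analysis, so there is none to reproduce. Let k be the share of an arm that completes DB without entering SB, and d the share of the others who stop by Week 36. Neither is given in the documents; both are assumptions.

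- Stopping with every stop counted: k + (1-k)d
- Kaplan-Meier under the SAP rule: about d
- Understatement: k + (1-k)d - d = k(1-d)

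For k = 1%, this gives 1 × 0.90 = 0.9 points at d = 10% and 1 × 0.70 = 0.7 points at d = 30%. For k = 2% and d = 15%, the curve shows 15.0% against 2 + 0.98 × 15 = 16.7%.

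**Step 3: product-limit check on one arm.** "Ultimately, 730 subjects were randomized" (SAP section 2.1), so at 1:1:1 an arm has 730/3, about 243 subjects. Assume 12 discontinue in DB. That is 5%, borrowed from the share expected in section 6.2.2 to lack a Week 4 reading, as an upper illustration. Assume also that about 20% of those entering SB discontinue there. Let c be the number who complete DB without entering SB.

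Worked case, c = 5, so 243 - 12 - 5 = 226 enter SB and 45 of them stop:

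- SAP rule: survival = (231/243) × (181/226) = 0.7613, so 23.9% stopped
- Counted as events: survival = (226/243) × (181/226) = 0.7449, so 25.5% stopped
- Difference: 1.6 points. The closed form agrees: k = 5/243 = 2.06%, d = 57/238 = 23.9%, and k(1-d) = 1.6 points

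| c | Day 28: SAP rule / counted | Day 252: SAP rule / counted | Day 252 difference (unrounded values) |
|---|---|---|---|
| 0 | 4.9% / 4.9% | 23.9% / 23.9% | 0 |
| 2 | 4.9% / 5.8% | 24.0% / 24.7% | 0.7 |
| 5 | 4.9% / 7.0% | 23.9% / 25.5% | 1.6 |
| 12 | 4.9% / 9.9% | 24.0% / 28.0% | 3.9 |

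With DB discontinuation varied over 2 to 5% and SB discontinuation over 10 to 30%, the Day 252 understatement is 0 for c = 0, 0.6 to 0.7 points for c = 2, 1.4 to 1.9 for c = 5 and 3.5 to 4.4 for c = 12.

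**Step 4: Cox model.** In the worked case the DB interval holds 12 events in the arm under the SAP rule and 17 if the boundary stops count. Section 8.2.4 says that the two-step model brings every event into the analysis. That is true only of stops coded as events. The direction of any change in a hazard ratio cannot be known, because it depends on how c differs between arms.

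**The case against.** The strongest reply is that the case may not arise. Events follow the treatment log, whose listed reasons include withdrawal by the subject and a residual category. A site may log a refusal to enter SB as Discontinued in DB, and the subject is then already an event. Section 2.1 and the footnote to Table 2 on end-of-treatment visits also read as if any stop before Week 48 is premature. This stands as a limit on size: nothing in the documents shows that even one such subject exists. It does not remove the problem, because 5.5.1 expressly provides for completers without SB treatment and sends them to censoring.

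It may also be said that the DB drop-out in 5.1.1 is a flow category, while 5.1.3 gives a separate part-by-part definition that 5.5.1 follows. That is correct. The drop-out count also includes subjects who discontinued during DB and randomized subjects never dosed, so it need not equal the number of events in the curve. A reader might infer that any mismatch between the two is an error, and the documents do not support that. The narrower inconsistency remains: an endpoint spanning both parts leaves out a permanent stop between them.

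The information is partly visible elsewhere. The disposition graph will show subjects not entering SB, and the weekly table beside the curve will show censoring around Week 4. A careful reader could notice the gap, but the curve and the hazard ratios would not reflect it.

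Finally, not continuing into SB is arguably different from stopping early within DB, so counting it changes what the event means. That is fair, and it is a reason to report the number separately.

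**Conclusion.** The point holds as a flaw in the definition of a descriptive analysis. Under the stated rule, a treated subject who completes DB and never starts SB is censored although treatment has permanently stopped. For each 1% of an arm affected, the Week 36 curve understates stopping by roughly 0.7 to 0.9 percentage points, assuming that 10 to 30% of the others stop. If nobody is affected, the error is zero.

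Three stronger conclusions are tempting and not supported. The first is that retention in this trial is overstated: the number affected is not given and depends on log coding. The second is that the arms differ at the boundary: no data in the documents bear on this. The third is that efficacy conclusions are touched: the analysis lies outside the testing strategy in section 6.1, and the primary and key secondary estimates, alpha and power do not depend on it. Priority is low.

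**What to change.** In section 5.5.1:

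1. Count SAF subjects who did not enter the SB part as events at the last DB dose. The restriction to the SAF is needed because a randomized subject who was never dosed has no last DB dose.
2. Censor at the last SB dose only subjects who completed SB treatment.
3. Report by arm the number who completed DB and did not enter SB.
4. In the two-step Cox model, use the subject-level cut-point that section 8.2.4 already allows, set at the DB treatment end day. A fixed cut at 28 days would move some of these stops into the SB interval: the addendum lets Visit 6 fall up to one week late, that is, to Day 28 + 7 = 35.

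The cost is a short rewording of the censoring rule and one derivation, with no effect on study conduct. Reported retention may become slightly less favourable, and the event will then cover not continuing into SB as well as stopping within a part. The count in item 3 lets a reader separate the two.
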